#### Secondary endpoints

- B) Psychosocial well-being
  - 1) Functional health status EQ-5D-3L (12 to ≤25yrs)
  - Diabetes specific quality of life: PedsQL Child version (<13 yrs), Adolescent version (13 to <18yrs) and young adult version (18 to ≤25yrs).

  - Fear of hypoglycaemia: Hypoglycaemic Fear Survey-II Worry scale: 17-≤25years. Children's Hypoglycaemia Fear survey 12 to <17yrs.

  - 4) Impact and Satisfaction: The Diabetes Technology Questionnaire, Baseline and Follow-up version (all ages)
  - 5) Diabetes distress: Problem Areas in Diabetes (Paediatric version 12 to <18yrs, Standard version ≥18yrs, Parent version)
  - 6) Hypoglycaemia Awareness: Hypoglycaemia Awareness Scale (Gold Score) (all ages)
  - 7) Generalized Anxiety Disorder-7 and Patient Health Questionnaire-9 (12 to 25 years)
  - 8) INSPIRE: Perceived benefits and burdens of automated insulin delivery (all ages Intervention only)
  - 9) Physical activity: The Active Australia Survey (all ages)
  - 10) Semi structure interview (all ages post study only)
- C) *Glycaemic outcomes:* -Percent time in range
- D) -CGM data: (time in hypoglycaemia, time in range, and time in hyperglycaemia)
  - a. % CGM Time <2.8 mmol/L
  - b. % CGM Time <3.3 mmol/L
  - c. % CGM Time <3.9 mmol/L
  - d. % CGM Time 3.9-7.8 mmol/L
  - e. % CGM Time >10.0 mmol/L
  - f. % CGM Time >13.9 mmol/L
  - g. % CGM Time >16.7 mmol/L
  - h. Standard Deviation and Coefficient of Variation of CGM values
- E) Changes in retinopathy scores and retinal microvascular structure (arteriolar or venular dilation, increased vascular fractal dimension, branching and tortuosity)
- F) Human factors:

Describe participant technology interaction, adherence patterns and approaches to improve interaction.

G) Health-economic

Report the health economic impact of the MiniMed ™ 670G / 780G Insulin Pump Hybrid Closed Loop System Vs standard therapy. The following data points will be used as part of the economic analysis:

- 1) QALYs calculated from the EQ-5D-3L
- 2) Hypoglycaemic events and HbA1c
- 3) Participant reporting on work interruption
- 4) Investigator reporting time spent on training, education and support, by the type of health professional resource used
- 5) Diabetes management consumables (glucose strips, ketone strips, batteries, sensors, site dressings, lancets, needles, insulin).

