#### VISIT 1: 1-2 hrs . (Eligibility Confirmation, Baseline data collection).

Information sheets will be provided in advance to participants who potentially fit inclusion criteria. Participants will be checked if they meet the inclusion criteria listed in Section 5.2. All post menarche females will have a urine  $\beta$ HCG test to exclude pregnancy. The following data will be recorded:

- 1. Consent signed by participant and investigator
- 2. Auxological
  - a. Height
  - b. Weight
  - c. BMI
  - d. Blood pressure
- 3. Demographic
  - a. Date of Birth
  - b. Gender
- 4. Diabetes clinical
  - a. Date of diagnosis
  - b. C-peptide (<0.1nmol/L cut off within 3 month of screening visit)
  - c. HbA1c
  - d. βHCG for all post menarche females
  - e. History of severe hypoglycaemia coma or convulsion or episodes requiring third party assistance (events in last 12 months).
  - f. History of diabetic ketoacidosis in the last 12 months
  - g. Hospital admissions in the last 12 months (DKA, Hyperglycaemia, Hypoglycaemia, Non diabetes related)
  - h. Total daily dose of insulin (mean of previous 7 days)
  - i. Co-morbidities and medications
  - j. Smoking and alcohol intake
  - k. Sensor data in the 2 weeks prior to the study (in participants on CGM).
- 5. Psychology measures:

Psychological scales will be administered on an electronic platform.

- a. Functional health status: Quality of Life: EQ-5D-3L for 12 to ≤25yrs
- b. Diabetes specific quality of life: PedsQL Child version (<13 yrs), Adolescent version (13 to <18yrs) and young adult version (18 to ≤25 yrs)

- c. Fear of hypoglycaemia: Hypoglycaemic Fear Survey-II Worry scale: 17 to ≤25yrs. Children's Hypoglycaemia Fear survey 12 to <17 yrs.
- d. Impact and Satisfaction: Diabetes Technology Questionnaire, Baseline version (all ages)
- e. Diabetes distress: Problem Areas in Diabetes (Paediatric version 12 to <18 yrs, Standard version ≥18 yrs, Parent version)
- f. Hypoglycaemia Awareness: Hypoglycaemia Awareness Scale (Gold Score) (all ages)
- g. Generalized Anxiety Disorder-7 and Patient Health Questionnaire-9 (12 to 25 years)
- h. Physical activity: The Active Australia Survey (all ages)

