#### VISIT 3 (4-6 hours)

This visit is the randomisation visit, and allocation is dependent on the stratifications detailed in Section 4.3.

The following data will be collected prior to randomisation:

- 1. Diabetes clinical
  - a. HbA1c
  - b. Total daily dose of insulin (mean of previous 7 days)
  - c. Severe hypoglycaemia in the run-in period
  - d. Diabetic ketoacidosis in the run-in period
  - e. Admissions in the run-in period
  - f. Pump upload
  - g. Sensor data in the 2 weeks prior to the study (in participants on CGM)
- 2. Diabetes education/review
  - a. Diabetes education: Diabetes educator session (2 to 4 hrs) as refresher to re-educate and optimise standard diabetes management
  - b. Carbohydrate Counting: Dietician review (1 to 2 hours)
     The duration of the session is variable according to the prior knowledge of the participant.
- 3. Retinal photographs, will be collected and retained for centralised assessment
- 4. INSPIRE questionnaire (baseline for participants randomised to AHCL)
- 5. Medtronic AHCL System Background Patient Questionnaire (optional)

6. Biomarkers

A detailed description of sample preparation for biomarkers is found in appendix

- 12mL of blood and 50mL of urine will be collected in fasting state
- a. Cell Adhesion Molecules (CAM)S
- b. Soluble vascular cell adhesion molecules sVCAM
- c. Soluble intercellular adhesion molecules sICAM
- d. s-e Selectin
- e. Oxidized Low density lipoprotein
- f. Myeloperoxidase.
- g. MicroRNA signatures for arterial, renal and retinal complications
- h. Telomerase
- i. DNA methylation/acetylation
- j. Glycomark
- k. Isoprostanes and proteomics
- I. Clotting profile

VISIT 4 (participants randomised to AHCL arm)

CSII to AHCL: Participant 780G, CGM education and AHCL training.

Visit 4A: Pump training (2 hours)

Participants will be trained on how to use the Medtronic 780G insulin pump. Participants will be provided with Roche Accu-Chek®glucometer along with the glucose strips for the study.

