#### Visit 4C: Commencement of AHCL (1 hour)

Once CGM data has been established for a minimum of 3 to 7 days, participant returns for face-toface instruction on AHCL use and initiation of Automode. During this visit, the sensor will be replaced to demonstrate sensor warm up and AHCL initiation, and provide an opportunity for those unfamiliar with CGM use to practice a sensor change with supervision. Upon AHCL initiation, participants will be instructed to avoid excessive exercise for 48hrs while the algorithm adapts. Participants will subsequently have weekly communication via phone call or email for support for the following 4 weeks, and upload their pump weekly. Investigators will log all time spent training and in communication with participant. Communication can be more often – as per clinical need, and logged. Visit 4D: Review of AHCL (after 4 weeks from commencement of AHCL, 1 hour) Face-to-face meeting to upload insulin pump, review CareLink reports and revise settings (CHO ratio and Insulin action time)

Participants will be issued with enough consumables for the study.

Visit 4 (participant randomised to control arm) (10 weeks after randomisation)

Visit 4A: First blinded sensor insertion

Visit 4B: Removal of blinded sensor and second blinded sensor insertion

VISIT 5 (12 weeks after randomisation; 1 hour)

The following data will be collected at the midpoint:

1 Auxological

Height, Weight, BMI, Blood pressure

- 2. Diabetes clinical
  - a. HbA1c
  - b. Total daily dose of insulin (mean of previous 7 days)
  - c. Pump upload (for both groups)
  - d. Sensor data in the 2 weeks prior to the study visit (in participants on CGM)
  - e. Clinical review
- 3. Psychological assessments
  - a. Functional health status: Quality of Life: EQ-5D-3L for 12 to ≤25yrs
  - b. Diabetes specific quality of life: PedsQL Child version (<13 yrs), Adolescent version (13 to <18 yrs) and young adult version (18 to ≤25 yrs)

  - c. Fear of hypoglycaemia: Hypoglycaemic Fear Survey-II Worry scale: 17 to ≤25yrs. Children's Hypoglycaemia Fear survey 12 to <17 yrs.
  - d. Impact and Satisfaction: Diabetes Technology Questionnaire, follow-up version (all ages: only for AHCL)
  - e. Diabetes distress: Problem Areas in Diabetes (Paediatric version 12 to <18 yrs, Standard version ≥18 yrs, Parent version)
  - f. Hypoglycaemia Awareness: Hypoglycaemia Awareness Scale (Gold Score) (all ages)

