#### Risks associated with Paracetamol use:

• False elevation of sensor glucose readings. The level of inaccuracy depends on the amount of paracetamol active in the patient's body and may be different for each person.

Note: If participant is using paracetamol or medications containing paracetamol (e.g. cold, pain, fever, and cough medications) while in Auto Mode:

- Participant will be instructed by the study doctor not to use sensor glucose readings to make treatment decisions until participant has stopped using products that contain paracetamol
- Participant should take additional blood glucose meter readings to verify glucose levels.
- Participant should turn off Auto Correction.
- Participant should consider exiting Auto Mode.
- 8.2 The **safety parameters** and the methods and timing for assessing, recording, and analysing safety parameters. Include a description of emergency procedures if applicable.

This is a cohort of participants with poor glycaemic control and sub-optimal adherence to treatment and safety measures will be put in place.

- a. Participants will be contacted on a weekly basis (or more frequently as required) for at least 4 weeks after commencement of AHCL to review progress.
- b. Participants with high blood/sensor glucose levels will be advised to test for blood ketones.

Participants in the control group will be advised to follow the clinical pathway while participants in the intervention group will be advised to contact the research doctor/diabetes educator.

- c. . In the event of device (pump) failure, the participant will be advised to switch to their standard pump therapy and contact the research doctor/diabetes educator.
- d. Participants in the intervention group will be informed to contact the research diabetes educator if they experience technical issues with the sensor and/or system
- e. Patients are educated regarding awareness of insulin infusion failure (rising blood glucose levels and ketones) and how to manage this (using standard injected subcutaneous insulin, and change insulin infusion set).
- f. At each clinic visit, data will be forwarded to the principal investigator. Any admissions to hospital for DKA or severe hypoglycaemia will reported to the principal investigator with 24hrs.
- g. Establishment of Data and Safety Monitoring Board (DSMB) to review progress

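### Severe hypoglycaemia, DKA and admissions are itemised before randomisation but not at Visits 5 or 8, and early research contact differs by arm, so events that depend on being reported may be under-recorded in control

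*Protocol*

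**What the plan says.** **Before randomisation.** In Protocol section 4.2, the Visit 1 list takes a 12-month history of severe hypoglycaemia, of DKA ("History of diabetic ketoacidosis in the last 12 months") and of hospital admissions by cause. The Visit 3 list, completed before allocation, repeats all three for the run-in, for example "Severe hypoglycaemia in the run-in period".

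**After randomisation.** The clinical lists for Visits 5 and 8 hold HbA1c, insulin dose, pump and sensor data and an unexplained clinical review. Visit 8 adds pump ratios and sensitivity factors. Neither lists any of the three event items. The extension lists (Visits 10 and 11) do not either.

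**Contact.** AHCL participants attend Visits 4A to 4D. After AHCL starts, "Participants will subsequently have weekly communication via phone call or email for support for the following 4 weeks"; section 8.2 makes this at least four weeks. Controls are first scheduled to be seen at week 10, for a blinded sensor.

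**Reporting.** Section 8.2(b), on high glucose and ketones, says: "Participants in the control group will be advised to follow the clinical pathway while participants in the intervention group will be advised to contact". The contact named there is a doctor or educator on the study team. Section 8.2(f) has "Any admissions to hospital for DKA or severe hypoglycaemia" go to the principal investigator within 24 hours. Serious events are reported within 24 hours of notification. Section 8.4 counts severe hypoglycaemia needing third-party help as a severe adverse event. Its heading covers procedures for eliciting reports, but its text gives only definitions.

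**Use.** Among the health-economic inputs, section 4.1(G) lists "Hypoglycaemic events and HbA1c".

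**The concern.** The Protocol treats these three items as worth asking at baseline and again at the end of the run-in, then drops them from the lists at the point where the arms start to differ. What remains is passive capture: an event is recorded if someone on the study team hears of it. In the first ten weeks the chance of being heard is not the same in the two arms, and nobody is blinded.

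The exposed event is severe hypoglycaemia managed at home or school with another person's help. It meets the Protocol's definition of a severe adverse event but need not lead to an admission. If it is recorded less often in control, AHCL would look less safe than it is in the 6-month comparison, and the hypoglycaemic-event input to the economic analysis could shift the same way. With 50 participants planned in total, a few missed events could change the safety table. An analysis plan cannot recover events that were never asked about.

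**Working it through.** The Protocol gives no event or capture rate, so there is no stated figure to reproduce. The check is mainly textual.

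**Step 1. Event items by visit (section 4.2).**

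| Visit | Timing | Severe hypoglycaemia, DKA, admissions listed? | Clinical review listed? |
|---|---|---|---|
| 1 | before randomisation | yes, last 12 months | no |
| 3 | before randomisation | yes, run-in | no |
| 5 | week 12 | no | yes, undefined |
| 8 | week 26 | no | yes, undefined |
| 10 | extension | no | yes, undefined |
| 11 | extension | no | no |

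**Step 2. Scheduled study contacts after randomisation.**

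- AHCL before week 10: Visits 4A, 4B, 4C and 4D plus four weekly contacts = 4 + 4 = 8 (7 if 4A and 4B are combined).
- Control before week 10: 0.
- AHCL to week 26: 8 + Visits 5, 6, 7 and 8 = 12 (11 if combined).
- Control to week 26: Visits 4A and 4B + Visits 5, 6, 7 and 8 = 6.

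The difference is 8 against 0 before week 10 and 4 against 6 from then on. The imbalance is therefore an early one and does not run through the whole six months.

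**Step 3. Which route would catch a third-party-assisted episode without admission?**

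- Section 8.2(f): no, it covers admissions.
- Serious-event reporting: yes in principle, but the duty starts from notification.
- Visit lists: no item asks.
- Support contacts: an opportunity to mention it, in the AHCL arm only.

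**Step 4. Illustrative size.** With equal true rates, the observed AHCL:control ratio is the ratio of the capture probabilities. Taking 90-95% on AHCL and 60-80% on control (assumptions, not Protocol figures):

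- smallest: 0.90 / 0.80 = 1.13
- largest: 0.95 / 0.60 = 1.58

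**Step 5. The DKA stopping rule (section 4.9).** The rule acts when the AHCL count of severe DKA exceeds the control count by 5 or more. Assume 25 per arm, equal true risk and full capture on AHCL. The exact two-binomial probability of a recorded excess of at least 5 is:

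| True risk | Control capture 100% | 80% | 60% |
|---|---|---|---|
| 4% | 0.0012 | 0.0014 | 0.0016 |
| 10% | 0.017 | 0.024 | 0.035 |
| 20% | 0.055 | 0.097 | 0.164 |

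The effect is negligible at low risk. It becomes material only if severe DKA is common and is also often missed in control.

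**The case against.** The strongest reply is that control capture is unspecified rather than absent. The schedule in section 4.8 marks diabetes clinical data at Visits 5, 8, 10 and 11, and that heading carried the event items at Visits 1 and 3. Visits 5 and 8 include a clinical review in both arms, and section 6.3 mentions one every three months. Severe-event reporting is not limited to one arm and does not require an admission. The case report form, not shown here, may well ask at each visit.

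This stands as far as it goes, and it keeps the point modest. It does not close the gap. The visit lists that spell out the clinical data hold no event item after Visit 3. The schedule's clinical-review row is labelled as a review of pump and CGM data. Section 8.4, where an elicitation procedure belongs, has none.

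A reader might also infer several stronger things that the Protocol does not support:

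- *That controls are told to report hypoglycaemia by a different route.* The sentence in section 8.2(b) concerns high glucose and ketones, and the items after it concern device and technical faults. No arm-specific route for hypoglycaemia is stated.
- *That weekly contact lasts throughout the trial.* It is stated for at least four weeks after AHCL start.
- *That DKA counts, and so the stopping rule, are distorted.* Admissions for DKA are reportable within 24 hours without restriction by arm, so severe DKA leading to admission is the event least likely to be missed.
- *That the extension comparison is biased.* Controls who opt in start AHCL with the same weekly contact, so Visits 10 and 11 are not a randomised comparison.
- *That the economic input is definitely affected.* Section 4.1(G) names hypoglycaemic events without saying severe or non-admitted, so this link is an inference.

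**Conclusion.** The concern holds as a risk of unequal ascertainment in the primary phase. It is concentrated before week 10 and falls chiefly on severe hypoglycaemia that needs third-party help without admission. It rests on two facts in the text: the event items are absent from the Visit 5 and Visit 8 lists with no elicitation procedure in section 8.4, and scheduled contact before week 10 is about 8 against 0. The likely direction is against AHCL.

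The size cannot be derived from the Protocol. The range of 1.13 to 1.58 depends wholly on the assumed capture rates and shows only what such rates would imply. This does not invalidate the safety comparison; it calls for a cheap improvement that is worth making.

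**What to change.** - **Visit lists.** Add the three Visit 3 items (severe hypoglycaemia, DKA, admissions) to the Visit 5 and Visit 8 lists, worded as since the last visit and identical in both arms. Because the Visit 4 sessions fall at different times in the two arms, define that as the last visit at which the items were asked: Visit 3 for Visit 5, and Visit 5 for Visit 8. Add the same items to Visits 10 and 11 for the descriptive extension safety data.
- **Section 8.4.** State this as the elicitation procedure.
- **Use of the data.** Base the 6-month between-arm safety table and the hypoglycaemic-event input to the economic analysis on the visit-elicited events.
- **Leave alone.** Keep 24-hour reporting as it is. The DSMB should see every event from any source, with the source flagged. Restricting its counts to visit-elicited events could delay a stopping rule that applies at any time.

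**Cost.** Three extra case report form questions at visits that both arms already attend, and some recall error over about three months (weeks 0 to 12 and 12 to 26). Recall may not be exactly equal, since AHCL support calls could prompt memory, but the question and the interval would be.

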# 8.3 Details of the **Data and Safety Monitoring Board**, or equivalent. For further information refer to the TGA "Note for Guidance on Good Clinical Practice (CPMP/ICH/135/95)" 2000.

To safeguard the interests of the trial participants, monitor the main outcome measure including safety and efficacy, and monitor the overall conduct of the study, DSMB will be established. The board will receive and review information on the progress and accruing data and provide advice on the conduct of the trial to the Investigators. The DSMB will inform the Lead Investigator if, in their view, the results are likely to convince a broad range of clinicians, including those supporting the trial and the general clinical community that, on balance, one trial arm is clearly indicated or contraindicated for all participants or a particular category of participants.

8.4 The procedures for eliciting reports of and for recording and reporting **adverse events**. Include definitions of adverse events. For further information on adverse events refer to the TGA "The Australian Clinical Trial Handbook" 2006.

#### Adverse Event

Any undesirable clinical occurrence in a participant whether it is considered to be device related or not, that includes a clinical sign, symptom or condition and/or an observation of an unintended technical performance or performance outcome of the device.

#### Adverse Device Event

A clinical sign, symptom or condition causally related to the device implantation procedure, the presence of the device, or the performance of the device system.

#### Severe adverse events

- 1. Severe Diabetic ketoacidosis (venous ph <7.2)
- 2. Severe hypoglycaemia (seizure or coma or episodes requiring third party assistance)
- 3. Results in death, is life-threatening
- 4. Requires inpatient hospitalization
- 8.5 The type and duration of the **follow-up** of participants after adverse events.

The follow-up of participants after adverse events will follow standard clinical care pathway of the institution.

#### 9. Data Management, Statistical Analysis and Record Keeping

9.1 Description of the statistical methods to be employed, including timing of any planned interim analysis.

#### Primary study phase

Data collected and baseline and Visit 8 (i.e. prior to 'extension phase') will be used to assess the effectiveness of AHCL therapy as compared to standard therapy.

The primary analysis will assess differences in time in range (%) with hybrid closed-loop versus standard therapy, measured six months post-randomisation using analysis of covariance (ANCOVA) with adjustment for baseline time in range. Least square means and least square mean differences and their associated 95% confidence intervals will be presented for each treatment group and between groups.

Model residuals will be used to assess model fit. If the residuals indicate poor model fit, the outcome variable will be transformed and the model refitted and evaluated. If poor model fit cannot be addressed, nonparametric analysis will be performed. In the event that residuals are not normally distributed: the Mann–Whitney–Wilcoxon (Wilcoxon Rank-Sum) Test will be employed if raw data are symmetric; if raw data are non-symmetric, bootstrap methods will be used to test the difference between groups.

Continuous secondary outcomes (glycaemic, auxological, clinical, psychosocial) will be analysed using the ANCOVA approach described above.

Secondary analysis for outcomes collected at multiple time points will be conducted using linear mixed models including random effects and various variance-covariance structures to account for non-independence. Akaike information criterion (AIC) will be used to determine the most appropriate model.

No interim analyses are planned apart from the DSMB safety review reported above.

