# AHCL arm: Medtronic MiniMed™ 670G 4.0 / 780G for 6 months OR

#### Conventional arm: Standard care for 6 months. This will be followed by an optional extension phase for another 6 months.

The study will be conducted at four tertiary paediatric diabetes centres (Perth Children's Hospital, WA, Westmead Children's Hospital, NSW, Women's and Children's Hospital, SA, and Royal Children's Hospital, VIC). A home visit may be offered for some visits which involve insertion or return of blinded sensors prior to randomisation, mid and end of the study. This provides a patient centric approach working within the parameters of local policies and procedures on home visits.

**Pre-screening**: HbA1c, and fasting C-peptide for eligibility will be required, to occur within 3 months of formal screening.

All participants on CGM are encouraged to wear their sensor in the weeks preceding Visit 1.

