  - f. Generalized Anxiety Disorder-7 and Patient Health Questionnaire-9 (12 to 25 years)
  - g. Physical activity: The Active Australia Survey (all ages)
  - h. INSPIRE questionnaire

4. Retinal photographs, performed as part of the routine annual screening, will be collected and retained for centralised assessment

5. Semi-structured interview: A random selection of participants at PCH, Perth will be offered semistructured interview within 4 weeks of completion of the study.

4.3 Measures taken to minimise/avoid bias, including randomisation and blinding.

Blinding is not possible, in this open label study. Minimisation will be used to allocate participants to study group based on the following balancing factors measured at baseline: age at Visit 1, HbA1c at Visit 1, and study site (MinimPy) (15). Participants will be allocated to the minimisation-preferred group with a probability to 70%. Minimisation is a method of ensuring excellent balance between

groups for known prognostic factors (16). Randomisation will be undertaken by the delegated persons at Perth Children's Hospital.

4.4 Maintenance of any blinding records or randomisation codes and procedures for breaking codes.

As this study is not blinded, the maintenance of breaking codes is not required.

4.5 Method of tracking implantable medical devices (if applicable).

Device serial numbers will be attributed to each study participant and recorded on an excel worksheet as they are issued. At the conclusion of the study, devices will be returned and checked off against the excel worksheet.

4.6 A description of the interventions or investigational product(s). For drug trials information regarding the dosage and dosage regimen, as well as a description of the dosage form, packaging, dispensing and labelling should be included.

The user manuals for 780G system are supplied electronically (they are large, and not appropriate for printing).

4.7 Accountability procedures for the investigational product(s) including the placebo(s) and comparator(s) (if applicable).

The study investigators will be responsible for patient safety during the study. The participants on AHCL will be contacted on a regular basis to monitor progress and help troubleshoot the problems.

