#### Extension phase

The extension phase will allow device access to all participants taking part in the study and will allow safety data to be collected over a longer period of time. The effects noted during this period are not of primary interest and the approach to analysing extension phase data will be largely exploratory.

We will describe the patterns in primary and secondary outcomes from 6 months to 12 months in Group A (receiving the intervention at both time points) and compare the 6-month post-intervention effect size in Group B to that observed in Group A during the primary study phase.

Primary and secondary outcome scores, paired differences, and their 95% confidence intervals will be presented.

9.2 The number of participants planned to be enrolled (if possible, include number at each site). Document the reason for choice of sample size, including reflections on (or calculations of) the power of the trial and clinical justification.

The power calculation is for a parallel study design with two groups of equal size.

The power calculation is for a parallel study design with two groups of equal size. Based on information in the WA population-based database and current data (de Bock et al, accepted JDST 2018), we expect a between group difference of 1.5% in HbA1c at 6 months with a SD of 1.7% for both groups. With alpha set at 0.05, 22 subjects would be required in each group to have 80% power to detect a difference of 1.5%. It is assumed the total dropout rate will be up to 15%, so we plan to recruit 50 subjects in total.

- 9.3 The level of significance to be used. P-values <.05 will be considered statistically significant and 2-sided P-values will be reported.
- 9.4 Procedures for reporting any deviation(s) from the original statistical plan (any deviation(s) from the original statistical plan should be described and justified in the protocol and/or in the final report, as appropriate).
   Any deviations to the original statistical plan will be reported to relevant ethics committees, governance committees, the Australia New Zealand Clinical Trial Register (ANZCTR), the DSMB and the manuscript.
- 9.5 The selection of participants to be included in the analyses (e.g. all randomised participants, all dosed participants, all eligible participants, or all evaluable participants).

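### Section 4.3 minimises on age, HbA1c and site, but the ANCOVA in 9.1 names only the outcome's baseline value; if those factors are prognostic the test is mildly conservative and some power is lost

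*Protocol*

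**What the plan says.** Section 4.3 of the protocol bases allocation on "balancing factors measured at baseline: age at Visit 1, HbA1c at Visit 1, and study site". The scheme is a biased coin: "Participants will be allocated to the minimisation-preferred group with a probability to 70" per cent. The same section justifies minimisation as a way to balance "groups for known prognostic factors", so the design treats the three factors as related to outcome.

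Section 9.1 (Primary study phase) compares time in range at six months "using analysis of covariance (ANCOVA) with adjustment for baseline time in range". It applies the same ANCOVA approach to the continuous glycaemic, auxological, clinical and psychosocial secondary outcomes. Nowhere does the protocol name age, HbA1c or site as a covariate.

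On size, section 4.2 says "The study will be conducted at four tertiary paediatric diabetes centres". Section 9.2 expects a "between group difference of 1.5% in HbA1c at 6 months with a SD of 1.7% for both groups" and concludes: "With alpha set at 0.05, 22 subjects would be required in each group to have 80% power to detect a difference of 1.5" percentage points. It then plans 50 recruits to allow for up to 15% dropout. Section 9.3 adds that "2-sided P-values will be reported".

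**The concern.** Minimisation makes the arms more alike on the chosen factors than chance would. If the factors predict outcome, the treatment estimate varies less from trial to trial. A model without them does not register that gain: their variation stays in the residual, and the standard error is computed as if allocation had ignored them. The interval is then wider than it need be and the true type I error falls below 5%. The precision that the allocation scheme was meant to buy goes partly unused.

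With 50 recruits and perhaps 42 or 43 completers there is little power to spare, and the same model serves many secondary outcomes.

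**Working it through.** **1. The plan's own figure.** With a difference of 1.5 and an SD of 1.7, two-sided 5% and 80% power, the normal approximation is n = 2 × (1.960 + 0.842)² × (1.7/1.5)² = 20.2, so 21 per group. The t-based calculation gives 21.17, so 22, with 81.6% power at 22. The stated 22 is reproduced. For dropout, 44/0.85 = 51.8, so 52 against the planned 50; equivalently 50 × 0.85 = 42.5 completers. That is close enough, and is not the point here.

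**2. Degrees of freedom.** For time in range, adding age (1), HbA1c (1) and four sites (3) takes 5. For an HbA1c outcome whose baseline is the Visit 1 value, HbA1c is already in the model, so age and site take 4.

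**3. Simulation of the time-in-range model.** From the protocol: 44 analysed, 4 sites, minimisation with probability 0.70, two-sided 5%. Assumed: age and HbA1c are split in two for the minimisation, and R² is the share of outcome variance left after baseline time in range that the three factors explain. The protocol does not give R², so a range is shown. The effect is 0.706 outcome SDs, which gives the planned model about the 80% power of section 9.2. There are 6,000 runs per row, so the Monte Carlo error of a 5% rate is √(0.05 × 0.95/6000) = 0.0028. Standard errors are in outcome SDs.

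| R² | Planned: model SE / true SD | Planned: type I error | Planned: power | With factors: model SE | With factors: type I error | With factors: power |
|---|---|---|---|---|---|---|
| 0 | 0.242 / 0.244 | 0.050 | 82% | 0.252 | 0.049 | 78% |
| 0.05 | 0.243 / 0.240 | 0.050 | 81% | 0.246 | 0.053 | 79% |
| 0.10 | 0.243 / 0.241 | 0.048 | 81% | 0.239 | 0.055 | 81% |
| 0.20 | 0.241 / 0.235 | 0.042 | 82% | 0.225 | 0.051 | 85% |
| 0.30 | 0.243 / 0.230 | 0.041 | 82% | 0.211 | 0.051 | 89% |
| 0.50 | 0.242 / 0.219 | 0.031 | 84% | 0.178 | 0.049 | 97% |

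The planned standard error is too large by 0.241/0.235 − 1 = 3%, 0.243/0.230 − 1 = 6% and 0.242/0.219 − 1 = 11% at R² of 0.20, 0.30 and 0.50. At 0.10 or below the discrepancy is about 1% or less.

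**4. Check on the break-even.** At R² = 0 the extra terms inflate the standard error by 0.252/0.242 = 1.041. Adding factors that explain R² should therefore multiply it by about 1.041 × √(1 − R²). At 0.30 that is 0.871, against 0.211/0.243 = 0.868 simulated. Setting the product to 1 gives R² = 1 − 1/1.041² = 0.08. Below about 8% the added terms cost precision, and a useful gain needs clearly more than 10%.

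**5. Is minimisation the cause?** With simple randomisation (probability 0.5) the planned model's type I error is 0.049 at R² = 0.30 and 0.049 at 0.50. The conservatism therefore comes from minimising on the factors and then leaving them out.

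**6. HbA1c scale.** A second simulation (4,000 runs, SD 1.7, baseline correlation 0.5, 44 completers) added only age and site. Their assumed effects are labelled only moderate and strong, so it supports the direction more than the size. Type I error without them was 4.3% and 3.7%. The standard error fell from 0.446 to 0.426 (moderate) and from 0.448 to 0.393 (strong). At the design difference of 1.5, a noncentral t with 41 and 37 degrees of freedom gives power of 91% to 93% (moderate) and 90% to 96% (strong).

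**The case against.** The strongest reply is that nothing in 9.1 is false. ANCOVA on the baseline value gives a valid test, and any departure is on the safe side. That stands: a reader might infer from the mismatch that false positives are inflated or that intervals under-cover, and the working shows the opposite.

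A reader might also infer that precision is certainly being thrown away and could be had for nothing. The documents do not support that. They call the factors prognostic but do not say how strongly, and what counts is what they add beyond the baseline value. Baseline HbA1c overlaps with baseline time in range, and a 70% coin weakens the effect: at R² = 0.30 the type I error is 0.041, against 0.033 under deterministic minimisation. If the factors add little, adjusting costs power.

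Third, 9.1 does not say that baseline is the only covariate, and an analysis plan could list more. This stands in part. But 9.1 does state the model, and an analyst following it as written would leave the factors out. The mixed models, for which 9.1 lists no covariates, are not part of this point.

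Fourth, section 4.1 makes change in HbA1c the primary endpoint while 9.1 analyses time in range. That conflict is separate and more serious. Under HbA1c, one factor may already be in the model through its baseline, which narrows this point to age and site but does not remove it.

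**Conclusion.** The point holds as a conditional loss of efficiency. Allocation uses three factors and the stated analysis names none of them for time in range. If they explain about 20 to 50% of the variance left after baseline, the planned test runs at about 4.2 to 3.1% instead of 5%, and power is about 3 to 13 points below that of the model with the factors. At about 10% the two models are level. At 0 to 5% the planned model is better by about 1 to 4 points. Moderate age and site effects on HbA1c gain only about 2 points at the design difference of 1.5.

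These sizes rest on assumed prognostic strength and on about 44 analysed participants. The direction of the miscalibration rests only on the factors being prognostic beyond baseline, as the choice of minimisation presumes. Validity is not in question.

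**What to change.** State in 9.1 that the ANCOVA includes the baseline value of the outcome plus Visit 1 age (continuous), Visit 1 HbA1c (continuous) and study site. Fit site as a random effect, or pool small sites by a rule fixed before outcome data are seen.

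For an HbA1c outcome, one baseline HbA1c term is enough provided the analysis baseline is the Visit 1 value used in minimisation. HbA1c is also measured at Visit 3 before randomisation, so the protocol should say which is the baseline. The rank-test fallback in 9.1 cannot carry these covariates, and the text should acknowledge that.

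The cost is one sentence and five degrees of freedom for time in range (four for HbA1c), worth about 1 to 4 points of power if the factors prove not to be prognostic. Make the change before outcome data are seen, since covariates chosen afterwards would be open to challenge.
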